### **6.3 Secondary Objectives**

Secondary objectives of this pilot study include the following:

- 1) Assess the frequency of cerebral desaturations in both the intervention and control cohorts by examining both the total number of patients experiencing any cerebral desaturation as well as the total number of events among patients experiencing any cerebral desaturation (of at least 5% below baseline and progressively larger desaturations). These analyses will be conducted on the entire study population as well as upon each cohort. The Area Under the Curve (AUC) analysis

technique [incremental desaturation categories will be assessed based upon 5 to 50% decreases, measured in 5% increments, from established room air baseline as well as oxygen supplemented pre-incision baselines as well as desaturations below absolute measured rSO2 values] will be employed to conduct these analyses.

- 2) Assess the frequency of adverse clinical events and serious adverse events overall and in each cohort.
- 3) Perform a comprehensive assessment of the frequency and efficacy of predefined rSO2 desaturation mitigation interventions and their collective ability to affect the observed cerebral oximetry values.
- 4) Assess the interventional cohort's preoperative demographics and collected covariates for association with the ease or difficulty of mitigating observed cerebral desaturation events.

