### 7.2.3 Intraoperative and Immediate Postoperative Period

The intraoperative period will occur immediately following completion of the Baseline Acquisition Period. Subjects randomized to the control group will be induced into general anesthesia with electronically blinded rSO2 monitoring while those randomized to the intervention cohort will undergo open rSO2 monitoring with the application of a standardized interventional protocol (Appendix D) for any observed significant cerebral desaturations. Significant cerebral desaturations are defined as any desaturation  $\geq 10\%$  of established room air baseline values for each individual subject. This period will continue through the end of the surgical procedure to PACU discharge or if the subject goes to the ICU through the first 12 hours of ICU admission.

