$AUC_{SpO_2} < 75\%$  regardless of intraoperative  $FiO_2$  values

$AUC_{SpO_2} < 70\%$  regardless of intraoperative  $FiO_2$  values

- Time from procedure completion to arrival in the post anesthesia care unit (PACU) or ICU
- Temperature upon PACU/ICU arrival
- Aldrete score upon PACU/ICU arrival and at 30 & 60 (or at discharge) min post-PACU arrival (See Appendix A)
- Any occurrence of immediate postoperative atrial fibrillation
- Any myocardial ischemia in the immediate postoperative period
- Any need for allogeneic RBC transfusion in the immediate postoperative period
- Any observed stroke or TIA in the immediate postoperative period
- Time to clinical readiness for PACU discharge as assessed by established institutional discharge criteria (see Appendix B)
- Frequency and severity of nausea and vomiting observed in the PACU and/or ICU as assessed by an accepted postoperative nausea and vomiting scale
- ICU length of stay (ICU-LOS) [anticipated to be at least 10-20 evaluable subjects for this parameter if 100 patients are enrolled] which will be defined as time to clinical readiness for ICU discharge as assessed by the clinical team caring for the patient
- Postoperative mechanical ventilation time if still intubated and admitted to the ICU following the surgical procedure
- Use of any immediate postoperative, intravenous vasopressor and/or inotropic agent (as assessed by amount of time in minutes on any IV drug support regardless of dose and assessed by total dose of drug delivered to patient)
- Immediate postoperative urine output in any patient with an indwelling foley catheter as assessed by mLs urine/kg/hr for total time in operating room
- Hospital length of stay (H-LOS)
- Need for skilled nursing facility/rehabilitation hospital admission upon discharge from index hospitalization
- Length of time spent in a skilled nursing facility/rehabilitation hospital upon discharge from index hospitalization if a relevant data point for each subject

- Need for hospital readmission for any reason within 30 days of surgical procedure
  - Observed change from preoperative baseline Mini-mental Status Examination (MMSE) score (including postoperative day #1 and postoperative day #3 or discharge scores)
  - Presence/absence of postoperative delirium (as assessed by the CAM Delirium assessment tool results obtained preoperatively and postoperatively upon PACU discharge, Day#1 and 3 [or hospital discharge])

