- Change in baseline renal function (as assessed by  $\Delta$ GFR from baseline compared to inhospital nadir postoperative GFR estimated by the Cockcroft-Galt method,  $\Delta$ preoperative serum creatinine obtained within 6 weeks of surgical procedure to nadir postoperative value and any new need for any form of renal replacement therapy)
- Postoperative use of epidural catheter
- Documented return of bowel function time (as assessed by time to first bowel movement following surgical procedure)
- Need for postoperative (any time from transfer from OR to discharge) red blood cell transfusion (as assessed by number of RBC units transfused)
- Occurrence of any postoperative (any time from transfer from OR to discharge) stroke or transient ischemic attack (as assessed by documented clinical neurological assessment or cerebral imaging study)
- Any observed postoperative (any time from transfer from OR to discharge) myocardial ischemia or infarction (as assessed by physical examination, intraoperative ECG changes and/or myocardial biomarkers [i.e. troponin increase])
- Postoperative (any time from transfer from OR to discharge) occurrence of any form infectious complication up to POD 30
- Postoperative time to wean from supplemental oxygen
- Postoperative (any time from transfer from OR to discharge) composite endpoint that includes any subject with at least one of the following: new onset atrial fibrillation,  $\geq$ Grade 2 PONV, HLOS $\geq$ 4.5 days, PACU LOS $\geq$ 2 hours, any infectious complication, death, stroke, myocardial infarction, greater 0.5 mg/dL increase in creatinine or new need for renal dialysis, postoperative need for intravenous inotropes or vasoactive medications

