## **10 TREATMENT OF SUBJECTS**

### **10.1 Study Device**

The study device, INVOS® 5100C, is described in Section 8. Enrolled subjects will be randomized in a balanced fashion (1:1) to either the control group (blinded cerebral oximetry monitoring intraoperatively and in the immediate postoperative period) or to the intervention group (open cerebral oximetry monitoring with the use of a standardized intervention protocol for observed desaturations greater than 20%).

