### **10.3 Intervention Group**

The intervention group will have baseline NIRS values obtained in a manner analogous to the control group. Following recording of the baseline values the subjects will be induced into general anesthesia and the clinicians as well as an IRB registered research assistant will be able to openly monitor the NIRS data. Upon observed cerebral desaturations greater than 20% of the oxygen supplemented baseline on either frontal hemisphere the research assistant will inform the anesthesia clinician that a significant cerebral desaturation is occurring and requires treatment. At this point a standardized interventional protocol will be followed that is detailed in Appendix C. The clinicians caring for the subject will have the ability to override the study intervention algorithm based upon the patient's physical condition at the time.

The intervention protocol for observed desaturations >20% will involve insuring that the subject's head vessels are not kinked or obstructed, increasing the mean arterial pressure via an intravenous fluid bolus or administration of a vasoconstrictor (i.e. phenylephrine or ephedrine) as deemed appropriate by the anesthesia clinician caring for the subject, normalizing PaCO2 to a value between 40 to 50 mmHg, or alternatively normalizing end tidal CO2 to a value of 35 to 45 mmHg. Subsequent interventions may include increasing the FiO2, especially if the SpO2 is below 98% or administering an intravenous inotropic agent if a low flow state is suspected. Administration of an inotrope will occur as judged by the clinician caring for the subject. Finally, in cases where the subject's hematocrit is known or suspected to critically low transfusion of allogeneic blood will be considered. The decision to transfuse allogeneic blood will be made by the anesthesia and surgery clinicians caring for the subject.

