## **11 PROTOCOL ASSESSMENTS AND PROCEDURES**

The Schedule of Assessments which details the sequence of assessments and procedures is presented in Table 1. Note that as described in Section 7.2 there are four separate periods that this study is divided into that include the following: screening, baseline, intraoperative and immediate postoperative and postoperative follow up.

Table 1: Schedule of Assessments

	Screening	Baseline Acquisition	Intraoperative and Immediate Postoperative	Postoperative Follow Up
Study Assessment				
Review of inclusion/exclusion criteria	X			
Informed consent	X			
Demographics	X			
Medical history	X			
Randomization		X		
MMSE & CAM testing		X		X
Serum creatinine	X			X
Obtain baseline room air and O 2 supplemented rSO 2		X		
Continuous rSO 2 , SpO 2 , blood pressure data collection			X	
Employ rSO 2 desaturation algorithm (intervention group only)			X	
Continuous intra/immediate post-operative clinical variable collection			X	
PACU and ICU clinical variable collection			X	
Postoperative clinical variable collection			X	X
Adverse and Serious Adverse Event Monitoring		X	X	X
Telephone interview				X

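### The composite counts postoperative inotrope or vasoactive need, but only the intervention arm follows an algorithm offering those drugs, so treatment may be scored as a bad outcome in one arm

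*Combined protocol and SAP*

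**What the plan says.** - **Composite (7.4.1.2).** One component is enough to make a subject an event, at any time from transfer out of the operating room to discharge. The last component is "postoperative need for intravenous inotropes or vasoactive medications". Need is not defined.
- **Monitored period (7.2.3).** The intraoperative and immediate postoperative period runs "to PACU discharge or if the subject goes to the ICU through the first 12 hours of ICU admission".
- **Who follows the algorithm (Table 1, section 11; section 10.1).** Table 1 places the desaturation algorithm in that period, for the intervention group only. Controls have "blinded cerebral oximetry monitoring intraoperatively and in the immediate postoperative period".
- **What the algorithm offers (10.3).** The steps include "administration of a vasoconstrictor (i.e. phenylephrine or ephedrine) as deemed appropriate by the anesthesia clinician caring for the subject", with a fluid bolus as the alternative, and later "administering an intravenous inotropic agent if a low flow state is suspected". Transfusion may be considered. Clinicians may override the algorithm.
- **Related endpoints.** Section 7.4.1.2 also lists "Use of any immediate postoperative, intravenous vasopressor and/or inotropic agent" by time and dose. Section 7.4.1.1 lists the intraoperative counterpart, crystalloid and colloid volumes, and red cell units.
- **Analysis (15).** The statistical plan has no rule on drugs given because of the algorithm.

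**The concern.** The composite window and the algorithm window overlap in the PACU and the first 12 ICU hours. In that overlap a desaturation can prompt a vasoactive drug in the intervention arm, whereas in the control arm nobody sees the reading. Controls can still receive these drugs as usual care, so the asymmetry lies in the trigger and not in access. Even so, the composite as written would score the delivered intervention as a failure in one arm.

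This matters because the pilot exists to choose endpoints for a larger trial. Section 6.2 looks for outcomes that differ significantly between arms; the synopsis (Criteria for Evaluation) looks for those that improve. Under section 6.2, an algorithm step could be selected as a relevant outcome. Under the synopsis, it could be read as harm or could hide a real benefit in the other components.

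Vasopressor and inotrope time and dose, fluid volume, and red cell transfusion during monitoring share the problem, because each is an algorithm step. The surgical-change item needs its wording reconciled. Section 11.3.3.1 ties it to rSO2, which blinded controls could not trigger. Section 7.4.1.1 refers only to an observed desaturation, which could be a fall in pulse oximetry in either arm.

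**Working it through.** The documents state no composite event rate, effect size or power, so there is no planned figure to reproduce. The calculation below is an illustration.

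**Inputs**
- 100 subjects randomized 1:1 (7.1), so 50 per arm.
- Significance at p < 0.05 (section 15, stated for the logistic regression). Two-sided testing is assumed.
- Assumed: the other components occur in 60% of controls and 42% of intervention subjects.
- Assumed: a share *q* of intervention subjects receives an algorithm-prompted vasoactive drug after leaving the operating room; *q* = 0, 2, 5, 10 or 20%.

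**Method.** Exact enumeration of two binomials, pooled z test, |z| > 1.96, each direction counted separately. On a yes/no outcome the tie-corrected Wilcoxon test named in section 15 is almost the same test: its variance differs by the factor 100/99.

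**Formulas for the observed intervention rate**
- A, independence, no usual-care use: 0.42 + 0.58*q*, against 0.60.
- B, 10% usual-care use in both arms: 0.42 + 0.58[1 − 0.9(1 − *q*)], against 0.60 + 0.40 × 0.10 = 0.64.
- C, 75% of those given the drug already have another component: 0.42 + 0.25*q*, against 0.60.

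Example for A at *q* = 10%: 0.42 + 0.58 × 0.10 = 0.478, and 0.60 − 0.478 = 12.2 points.

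| *q* | A: benefit (points), power | B: benefit (points), power | C: benefit (points), power |
|---|---|---|---|
| 0 | 18.0, 46% | 16.2, 39% | 18.0, 46% |
| 2% | 16.8, 42% | 15.2, 35% | 17.5, 44% |
| 5% | 15.1, 35% | 13.6, 29% | 16.8, 41% |
| 10% | 12.2, 25% | 11.0, 21% | 15.5, 36% |
| 20% | 6.4, 10% | 5.8, 9% | 13.0, 27% |

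Power is in the benefit direction. Under A the benefit vanishes at *q* = 0.18/0.58 = 31%.

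**No true effect (60% in both arms).** Under independence the intervention rate is 0.60 + 0.40*q*. With 75% overlap it is 0.60 + 0.25*q*.

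| *q* | Independence: excess (points), rejection for harm | 75% overlap: excess (points), rejection for harm |
|---|---|---|
| 0 | 0, 2.6% | 0, 2.6% |
| 2% | 0.8, 3.1% | 0.5, 2.9% |
| 5% | 2.0, 4.1% | 1.25, 3.5% |
| 10% | 4.0, 6.2% | 2.5, 4.5% |
| 20% | 8.0, 12.9% | 5.0, 7.5% |

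**Other assumed rates.** With 50% against 25% under the independence formula, the difference falls from 25 to 17.5 points at *q* = 10%, and approximate power falls from 74% to 43%. The pattern is the same.

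**The case against.** **Postoperative drug delivery is partly inferred.** Section 10.3 starts from induction, addresses the anesthesia clinician, and does not mention the PACU or ICU. The algorithm appendix is not in the text available here. Purely intraoperative use falls outside the composite. These points limit the likely size. But section 7.2.3 and Table 1 carry the algorithm past the operating room, and an infusion still running at transfer could plausibly count.

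**Need is not use.** The separate endpoint counts any use, while the composite counts need, which could mean clinical requirement. That reading is possible, but with no definition the same drug could be scored either way.

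**A real effect of the strategy is not bias.** If open monitoring leads to more vasoactive treatment, that is a genuine consequence and worth reporting. It is still a consequence for the treatment given, and does not by itself show a worse patient outcome.

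**The rates are invented.** This is true. Section 7.4.1.2 expects only about 10 to 20 subjects evaluable for ICU stay, so most exposure would be confined to the PACU. The composite has other components, such as hospital stay and nausea, that treated subjects may already meet. Case C shows how much this softens the loss.

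**Dropping the component loses later need, when no algorithm operates.** This is a fair cost. Counting only use after the monitored period would be narrower. However, the later follow-up list in 11.4.3.1 has no separate vasoactive item, and drugs started earlier may carry over. Excluding only algorithm-prompted use would require an attribution that can be made in one arm only.

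**Existing objectives already cover part of this.** Section 6.3 assesses the frequency and efficacy of "desaturation mitigation interventions and their collective ability to affect the observed cerebral oximetry values". That provides a place to report these steps; it does not remove them from the composite.

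**Conclusion.** The concern holds. Following the plan as written can score delivered treatment as a bad outcome through a trigger only the intervention arm has. The mechanical bias runs against open monitoring, although better oxygenation might lower later drug need and offset part of it.

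Its size cannot be estimated from the documents. Under the assumed rates it is small at 2% algorithm-prompted use. From about 10% it is material if drug use is independent of the other components, costing about 5 to 6 points of benefit. With 75% overlap the cost at 10% is 2.5 points. The actual share also depends on the trigger: section 7.2.3 refers to a fall of at least 10% from the room air baseline, sections 7.1 and 10.3 to more than 20% from the oxygen-supplemented baseline. Those sections must be reconciled.

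This should be changed before analysis. It affects one composite among many listed endpoints, but one that could steer the design of the larger trial.

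**What to change.** 1. Judge benefit on the composite without the inotrope/vasoactive component.
2. Report the composite with that component as a sensitivity analysis. Define need once, before analysis, and apply the definition identically in both arms.
3. Treat vasopressor and inotrope use, fluid volume and red cell units given during the monitored period, and rSO2-prompted surgical change, as process-of-care measures. Report them by arm alongside the intervention-frequency objective in 6.3, and do not use them as evidence of benefit or harm when choosing endpoints for the larger trial.
4. Reconcile the surgical-change wording in 7.4.1.1 and 11.3.3.1.

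The cost is endpoint and analysis wording. Immediate postoperative vasopressor and inotrope use is already collected (7.4.1.2, 11.3.3.2). The composite will have fewer events, by an unknown number, and any true reduction in vasoactive need will show only in the sensitivity analysis and the separate vasopressor item. No change to clinical care is proposed.

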## 8 STUDY DEVICE

### 8.1 Device Description

The INVOS® 5100C is a 2 wavelength, diffuse reflectance spectroscopy system employing near

infrared light to estimate the percentage of hemoglobin saturated with oxygen in tissue underneath the sensor. This is similar to the noninvasive technology widely used in pulse oximeters to monitor oxygen saturated hemoglobin percentage in arterial blood.

An adhesive sensor containing a light source and 2 photodiodes is applied to the skin over the tissue of interest and the returning light is analyzed for hemoglobin and deoxyhemoglobin light absorption. Absorption signals from the photodiode closer to the light source are subtracted from those from the farther photodiode where the returning photons penetrate more deeply in the tissue. This suppresses absorption events originating in the outer layers of tissue that are common to both photodiodes, including the effects of skin pigmentation and subcutaneous tissues.

The INVOS® 5100C tissue oximeter is a multichannel monitor with continuous recording and display of readings of regional tissue hemoglobin oxygen saturation from 4 separate sensors simultaneously. The monitor is connected to 2 preamplifiers, each of which in turn supports 2 sensors. It has USB connectivity for dynamic data capture, storage and transfer as well as a digital output port.

## **8.2 Indications for Use**

The noninvasive INVOS® 5100C is intended for use as a monitor which provides accurate, immediate feedback of regional hemoglobin oxygen saturation of blood in the brain or in other tissue beneath the sensor. It is intended for use in any individual at risk for reduced-flow or noflow ischemic states. The prospective clinical value of data from the INVOS® System has not been demonstrated in disease states. The INVOS® System should not be used as the sole basis for diagnosis or therapy.

## **8.3 Food and Drug Administration Status**

510K cleared (#K080769) April 2009

## **8.4 Technological Characteristics**

The INVOS® 5100C is an in vivo optical spectrometer using two wavelengths(730 and 810 nm) of near infrared light that is projected into any tissue beneath the sensor. A portion of the emitted light is reflected back to one of two fixed distance photodiodes (30 and 40 mm from the LED light source). Returning light signals are processed with a technique known as spatial resolution which permits removal of the majority of saturation data obtained in the more superficial scalp tissue and thus the final reading is thought to reflect primarily a venous weighted saturation (75% venous to 25% arterial) of hemoglobin below the sensor pads. The data processing occurs in the device preamplifier and is then sent to the display module for graphic display and storage. Device data can be directly transferred to a collection system via a serial cable or can be downloaded to a USB memory stick and further processed for analysis with an Excel® macros. The device has the capacity to simultaneously monitor, display and store 4 separate sets of monitoring data.

## 8.5 Device Image

## 8.6 Device Modification

The subjects randomized to the control group will be monitored with a modified device following the acquisition of the baseline NIRS data. The modification involves electronic blinding of the data via an adjustment made to the device by the manufacturer that prevents the active display of the current data and graphic trends on the display console. However, the modified device will still electronically store the acquired NIRS data for later analysis. The use of this modified version of the device will help to reduce investigator bias that might be introduced if a blinder were affixed to the display console.

# 9 SUBJECT SELECTION

## 9.1 Study Population

A total of 100 evaluable subjects will be enrolled into this protocol. Patients at least 65 years of age who are scheduled to undergo non-emergent, thoracic surgical procedures planned to involve the use of single lung ventilation will be evaluated in this study.

### 9.1.1 Inclusion Criteria:

1. Any male or female patient  $\geq 65$  years of age and able to provide informed consent (or consent may be provided by a legally authorized representative) who is scheduled for a thoracic surgical procedure that is expected to involve the use of intraoperative single lung ventilation (SLV)
2. Able to adequately complete a baseline mini-mental status examination (MMSE)

3. Able to complete a baseline confusion assessment method (CAM) examination
4. Able to obtain bi-frontal baseline rSO2 values prior to induction of anesthesia

